### Publications and communication of the results

### References

## Background and status of knowledge

*“Twelve billion working days are lost every year to depression and anxiety alone”.*

(WHO 2024)

Mental health problems and disorders affect one in every five amongst the working-age adults in the OECD countries (Kessler et al 2005). And as many as two thirds of new disability pensions are due to poor mental health (OECD 2016). This constitutes a major public health challenge that also has large implications for work participation and productivity. People with mental health conditions are more often unemployed, more often in need of sick-leave and are absent for longer durations (OECD 2020). People with mental disorders report a 30% lower employment rate than those with no mental disorders (OECD 2021). Of employees reporting mental disorders, half had days away from work, compared to under a third of people without mental ill-health. As many as two thirds of new disability pensions are due to poor mental health (OECD 2016). Mental health issues are also the largest cause of disability pensioning for adults from 25 - 39 years (Brage & Thune, 2020). Mental disorders as a cause of sick-leave and disability pension have increased in the OECD countries and Norway. Major depression and anxiety are the most prevalent of the mental disorders and are therefore named common mental disorders (CMD). CMD have become a major cause of work absenteeism, with 30% of all sick leave in Norway being due to CMDs in 2024, which is an increase from 20% in 2019 (NAV 2024; Gundersen & Medalen, 2019).

The option for paid sick-leave is an important tool and an effective way to stop deterioration when used correctly. However, long-term sick leave can also have adverse consequences (Folkehelseinstituttet, 2015). This seems especially relevant for people with mental disorders due to the adverse effects of absenteeism on mental health and negative

effects on workplace relationships due to the stigma associated with mental disorders (OECD 2016; Gundersen & Medalen).

While mental disorders are a major cause of prolonged sick leave (NAV 2020), return to work (RTW) has been shown to be positively associated with improved health, especially mental health (Folkehelseinstituttet 2015). Early interventions addressing psychological aspects and vocational challenges related to work have shown a positive effect on RTW (OECD 2014). Therefore, finding ways to increase availability and reduce barriers to evidence-based treatments seems a viable route to reducing mental health's impact on sick leave and absenteeism. It may be needed to give people on sick-leave not only treatment for their mental health symptoms, but also interventions that facilitate a planned return to work as an integrated part of the treatment process.

### **Treatment for people with common mental disorders on sick leave**

Although a reduction in symptoms of CMD seems positive for RTW the results are not straight forward. Findings from Cullen et al. (2012) show that improvement in symptoms from ordinary psychotherapy has little impact on sick-leave. The same results have been found for internet-based cognitive therapy (ICBT) by Udd-Granat et al (2023). One of the challenges in specialised mental health care is that the work focus has been an additive or extended part of the treatment, not integrated in the treatment itself. This is not in line with the recommendations for work-focused therapy (Slater et al., 2023) and might be the cause of the low impact on sick leave.

There thus seems to be a need for a focus on RTW within therapy. Several studies have been conducted on psychological treatments that specifically target return to work for people with CMDs. Systematic reviews have shown that work-focused therapy (W-CBT) has a small, but significant effect over treatment as usual on return to work (Mikkelsen & Rosholm 2018; Slater et al. 2023). Mikkelsen & Rosholm (2018) finds that 20% more

workers in the intervention groups had returned to work, compared to control groups. There is also evidence that some of the components in work-focused therapy are more important than others, namely: work related goal setting, work related psychoeducation, work-related behavioural activation with a gradual return to work plan, work related problem solving, work-related cognitive therapy and homework. (Mikkelsen & Rosholm 2018; Slater et al. 2023). Work-focused therapy, incorporating several of these efficacious components, has been studied in a Norwegian setting with good results on RTW (Reme et al. 2015; Gjengedal, et al. 2020).

### **Internet-delivered treatment for people on sick leave**

Another challenge for traditional psychotherapy is that access to treatment for CMD is lower than the demand (OECD 2016) and the treatment available varies greatly based on country of residence and if one is situated in an urban or rural area (Barbato, et al. 2016). Internet-delivered Cognitive Behavioural Therapy (ICBT) has the potential to increase accessibility to evidence-based treatment through increased availability and flexibility, while lowering cost and reducing need for travel for the patient. It has also been estimated that ICBT is cost-effective over traditional CBT mainly due to reduction in waiting time, which reduces time spent in an untreated state that may otherwise worsen the course of the illness (Baumann, et al., 2020; OECD 2016; Standal et al. 2021). Internet-delivered treatments have shown their effectiveness across several mental disorders, both with diagnosis-specific and transdiagnostic protocols (Etzelmüller et al. 2020, Taylor et al. 2021, Hedman-Lagerlöf et al. 2023). However, the impact of traditional symptom-focused treatment on sick-leave is suboptimal and in line with findings for traditional psychotherapy (Cullen et al. 2012; Cederberg et al. 2022; Udd-Granat et al. 2023). There is therefore a need for treatment

programs with an explicit focus on RTW using the efficacious components of work-focused therapy.

A further consideration is how to accommodate for the heterogeneity when the inclusion criteria is sick-leave. A transdiagnostic approach can be better suited for heterogeneous patient groups, as it targets common vulnerability factors rather than diagnosis-specific symptom clusters (Dalgleish et al. 2020).

### **Work-focused therapy in a digital format**

We identified three studies explicitly using W-CBT via an iCBT platform addressing work related stressors, for people on sick leave or in danger of absenteeism. These have used self-referrals and participants are recruited from a non-clinical setting, with mild to moderate symptoms. Two of these studies have focused on mental stress and its reduction to decrease or prevent absenteeism (Asplund et al. 2019, Persson et al., 2023). One also addressed the treatment of depression (Geraedts et al. 2014). Of the trials identified Persson et al. (2023) found a significant effect on work ability and short-term sickness absence using W-iCBT for stress. However, to the best of our knowledge no studies have investigated the effects of W-CBT in a digital format aimed at CMD where the population is in an out-patient clinic setting. Nor have we found a study using a transdiagnostic approach to W-iCBT.

### **Summary of knowledge**

The evidence that W-CBT delivered face-to-face improves return to work over CBT or treatment as usual on CMD seems strong (Mikkelsen & Rosholm 2018; Slater et al., 2023). There is growing evidence that CMDs can be effectively targeted using transdiagnostic models both face-to face (Sakiris & Berle, 2019; Schaeuffele et al., 2021) and via ICBT (Dear, Staples et al. 2015, Titov, Dear et al. 2015, González-Robles, Díaz-García et al. 2020, Schaeuffele, Homeyer et al. 2020). It also seems that the perceived level of self-efficacy towards return to work can be a good predictor for reduction in work absenteeism (Gjengedal

et al. 2021). The length of absenteeism predicts an increased risk of not returning to work (OECD, 2003; Blank et al., 2008; Roelen et al., 2012; OECD, 2021). There is some evidence that baseline treatment credibility is a predictor for both dropout, adherence and outcome in ICBT (El Alaoui et al., 2015; Alfonsson et al., 2016) and that treatment adherence predicts outcome (El Alaoui et al., 2015; Hedman et al. 2015).

### **Knowledge gap**

Current treatment is often targeting specific disorders without explicitly addressing RTW challenges and the coping strategies needed for RTW in the treatment packages. There is a need for studies that examine the potential contribution of interventions that integrate a systematic focus on work-related issues in a comprehensive therapeutic framework.

To the best of our knowledge there has been little or no research on a transdiagnostic cognitive behavioural therapy approach to work-focused therapy, nor a digital version of work-focused therapy for CMD targeting out-patients. The individual evidence of transdiagnostic ICBT and face-to-face W-CBT is compelling. An effective combination of these would be an important development towards increased availability of work-focused therapy. A small feasibility study on the program “eBehandling - Health and Work” performed by the authors have shown that the combination seems feasible, but there is a need for a larger scale study to determine the utility and use of the program for wider implementation. The potential contribution of this study is to explore the utility and feasibility of a broadly applicable treatment program for emotional disorders, that is built around RTW. There is also a need for more knowledge about the potential negative effects, as these have earlier not been adequately assessed in treatment research.

The single arm trial design aims to obtain preliminary results on treatment effects on RTW and clinical symptoms, as well as data on use and utility of the ICBT program as experienced by the patients. It is also the case that relatively little is known about what works

and for whom in the field of work-focused ICBT. This study aims to address this knowledge gap by exploring how common clinical and demographic factors impact treatment response.

### **Study aims**

The main aim of the current study is to investigate the utility and use of a digital transdiagnostic work-focused CBT treatment program for patients with common mental health disorders on sick leave or work assessment allowance. This includes the user experience of participation and experienced utility of the treatment program. Secondary aims are related to mediators and moderators of treatment efficacy and the participants' experience with the program.

### **Research questions**

1. To what extent does the treatment program impact Return to Work, self-reported symptoms, and everyday functioning?
2. To what extent do clinical, work-related and demographic factors affect treatment adherence and treatment response?
3. To what extent do adherence and changes in work-related self-efficacy predict outcomes?
4. What type and frequency of negative effects does participants report?
5. How do participants describe their experience of use and utility of the program, as well as its challenges and benefits?

## **Hypotheses of main effects**

**H1a.** We expect a large main effect of treatment on total percentage sick leave from pre- to post treatment, with gains maintained at follow up.

**H1b.** We expect a large main effect of treatment on the number of participants with full return to work from pre- to post treatment, with gains maintained at follow up.

**H2.** We expect a large main effect of treatment on reduction on symptoms of depression and anxiety.

**H3.** We expect a positive main effect of treatment on Return to Work Self-Efficacy, from pre to post treatment, and sustained through follow up.

## **Hypotheses of moderating and mediating effects and predictors of outcome**

**H4.** We expect a negative relationship between duration of baseline work absenteeism and degree of return to work at post. Baseline work absenteeism will moderate the relationship between treatment and return to work.

**H5a.** We expect treatment credibility at baseline to be predictive of treatment adherence.

**H5b.** We expect that treatment adherence will be a mediator between treatment credibility and treatment outcome.

**H6.** We expect changes on the Return to Work Self-Efficacy Scale to predict the degree of absenteeism post treatment.

**H7.** We expect change on the Return to Work Self-Efficacy Scale to be a mediator between baseline absenteeism and return to work post-treatment.

**H8.** We expect higher depression scores (PHQ-9/CORE-OM score) to be a moderator between treatment credibility and treatment outcome and adherence.

**H9.** We expect that fewer than 10% of participants experience negative effects caused by participation, as measured by the Negative Effects Questionnaire (NEQ).

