## Methods and procedures

### Design

This study is a non-randomized, single arm, multi-center mixed methods clinical trial in a naturalistic setting (see Figure 1 for an overview of the study design). Participants are recruited in a real life setting in Norwegian specialised mental health care. After recruitment participants fill out questionnaires pre, interim and post treatment, in addition to follow up at 6 and 12 months after completing treatment. Interim measures are collected after six weeks. After the treatment intervention, some participants are invited to an in-depth qualitative interview.

[figure not shown]

Figure 1. Study design.

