## Statistical analyses

**Quantitative analyses.** In order to identify factors associated with treatment success and outcomes, hierarchical linear mixed modelling analyses (HLM, “multilevel”) will be conducted. In longitudinal HLM, measurement occasions (time) are nested within participants. Fixed effects are average (main) effects, and do not vary across subjects. Random effects vary across subjects and/or measurement occasions (e.g., a random intercept model vs a random intercept, random slope model). In these models, data may be missing at random and at different occasions for different subjects (Tasca & Gallop 2009). The models will be checked if they fulfil the model assumptions of normality of residuals, linearity and homoscedasticity. The dependent variables are sick leave, work related self-efficacy (as measured by RTWSE-11), depression severity (PHQ-9), anxiety (GAD-7), well-being, symptoms, risk and function (CORE-OM) and impairment in functioning (WSAS). The predictors are: Treatment (time), duration of sick-leave prior to treatment, treatment credibility, work related self-efficacy, depression severity and adherence. Comparisons are modelled through main effect and interaction effect analysis (e.g. Time x “Baseline work absenteeism” interaction). Predictors will be centred using grand mean centering. T-values and degrees of freedom will be estimated using “Satterwaite” correction (Luke 2017). The effects sizes will be converted from *t*-values and degrees of freedom to Cohen’s *d* using the R-package “effectsize”. Estimating indirect effects (mediation), we will apply “causal mediation analysis” (CMA), that is a method to split a total effect of an independent predictor (X) into a direct (C) and indirect effect (M). The indirect effect is transmitted through a mediator to the outcome. CMA will be conducted under the assumption of sequential ignorability. The X will be measured at baseline, the M at intermediate treatment, and the outcome(s) at post-treatment (Zhang et al. 2016). See Figure 2 below for a tentative model.

[figure not shown]

Figure 2. Model of mediation.

Corrections for multiple analyses will be done by using Jaccard's correction (Jaccard, 1998) to decrease risk of Type I error when applying several statistical tests.

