## **Publications and communication of results**

The results will be published in high impact, international open access peer review journals. The titles of the planned papers are:

*Paper I:* The use and utility of a new digital transdiagnostic work-focused cognitive behaviour therapy program for patients on sick leave in specialised mental health care.

*Paper II:* Mediators and moderators for treatment utility of a digital work-focused therapy program.

*Paper III:* Participants experience with digital work-focused therapy – a qualitative study.

The results will be presented at international and national conferences. The PhD candidate in the study will contribute with popular science articles for user groups and the general population. Speeches and lectures will be given to relevant groups such as health care practitioners in specialised mental health care, municipal health care practitioners and relevant user organisations.

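### H4's moderation claim is not identifiable in one arm: the time-by-baseline-absence interaction cannot separate a weaker program effect from a slower natural return to work

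*Protocol*

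**What the plan says.** H4 (Hypotheses of moderating and mediating effects and predictors of outcome) has two sentences. The first is an association: "We expect a negative relationship between duration of baseline work absenteeism and degree of return to work at post". The second is a claim about effect modification: "Baseline work absenteeism will moderate the relationship between treatment and return to work".

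The Design section says: "This study is a non-randomized, single arm, multi-center mixed methods clinical trial in a naturalistic setting". There is no comparator.

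Statistical analyses sets out the model terms: "The predictors are: Treatment (time), duration of sick-leave prior to treatment, treatment credibility, work related self-efficacy, depression severity and adherence". Treatment is thus represented by time. The same section says: "Comparisons are modelled through main effect and interaction effect analysis", and its example is the interaction of time with baseline absenteeism.

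The background (Summary of knowledge) states: "The length of absenteeism predicts an increased risk of not returning to work". It does not tie this to the program under study.

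Knowledge gap describes the purpose: "The single arm trial design aims to obtain preliminary results on treatment effects on RTW and clinical symptoms". It also names the question of what works for whom. Study aims refers to moderators of efficacy, and the planned Paper II is titled "Mediators and moderators for treatment utility of a digital work-focused therapy program".

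**The concern.** A moderator of a treatment effect changes how much the treatment adds over its absence, so estimating it needs variation in treatment. Here there is none. The interaction of time with baseline absence compares the pre-to-post change of participants with short and long absence, all of them treated. If people with long absence return to work more slowly whatever is done, their sick leave falls less, and the interaction points the way H4 expects without any difference in what the program contributes.

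At stake is the conclusion. A significant interaction would count as confirmation of H4's second sentence, and so as evidence that the program works less well after long absence, when the data cannot show that. A larger sample does not help: it makes a significant result from prognosis alone more likely.

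**Working it through.** **1. What the coefficient contains.** Let X be baseline absence, D1 a participant's change in sick leave with the program and D0 the change the same person would have had without it. Then D1 = D0 + (D1 − D0), so

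slope of D1 on X = slope of D0 on X (natural prognosis) + slope of (D1 − D0) on X (effect modification).

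Only D1 is observed. The planned interaction estimates the sum, while H4's second sentence concerns the second term alone. With D1 = D0 for everyone, the second term is zero and the sum still differs from zero whenever prognosis depends on X.

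**2. The plan's own figures.** Power analyses gives no power or error figure for this interaction. Its nearest figure is 25 participants for one main effect (d = 0.6, power 0.8, two-sided 0.05). An exact paired t-test gives 23.8, rounded up to 24, and power 0.82 at 25, so that figure reproduces within rounding. It has no bearing on identification. Used below: the analysis target of 300, and 390 enrolled with 30% dropout, 390 × 0.7 = 273 completers.

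**3. Illustration with assumed return rates, zero treatment effect.** All of these are assumptions: n = 273, half with short and half with long absence; baseline degree of sick leave 50, 60, 80 or 100% with probabilities 0.25, 0.10, 0.15, 0.50; post score 0 if returned, otherwise unchanged; Welch test of change between the halves. With two waves and a short/long split, this stands in for the time-by-absence test.

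Mean baseline degree = 0.25×50 + 0.10×60 + 0.15×80 + 0.50×100 = 80.5. The expected difference in change is 80.5 × the gap in return rates.

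| Natural return, short vs long | Expected difference in change | Significant at 0.05 | Significant at 0.01 |
|---|---|---|---|
| 40% vs 20% | 80.5 × 0.20 = 16.1 points | 94% | 82% |
| 40% vs 25% | 80.5 × 0.15 = 12.1 | 71% | 47% |
| 35% vs 25% | 80.5 × 0.10 = 8.1 | 40% | 19% |
| 30% vs 25% | 80.5 × 0.05 = 4.0 | 14% | 5% |
| 30% vs 30% | 0 | about 5% | about 1% |

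The 0.01 column stands for the multiplicity correction that Statistical analyses plans. It is an assumed first-step threshold for five tests (0.05/5). Where natural return differed, nearly all significant results lay in H4's direction.

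**4. Check by a second route.** Take absence as continuous with correlation r to natural change, again with zero treatment effect. With two balanced waves the interaction test equals regressing change on X, with noncentrality r√N / √(1 − r²). At N = 273:

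- r = 0.10: 0.10 × 16.52 / 0.995 = 1.66, rejection 38%
- r = 0.20: 0.20 × 16.52 / 0.980 = 3.37, rejection 92%

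At r = 0.05 the rate is 13%, and at r = 0 it is 5%. At N = 300 the rates for r = 0.05, 0.10 and 0.20 are 14%, 41% and 94%.

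**5. Where the problem sits.** A further simulation at N = 300, with continuous absence duration and natural return of 35/35, 40/30, 45/25 and 50/20% (short/long), gave single-arm rejection of 5%, 22%, 69% and 96%. With a hypothetical concurrent control arm added, the arm-by-absence test rejected in 4% to 5% in all four cases. The excess comes from the missing comparator. The exact percentages depend on the model: a 10-point gap gives 22% here and 40% in step 3.

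**The case against.** **The design is openly single-arm and its results are called preliminary.** That is true, and the section heading above H4 also mentions predictors of outcome. But preliminary describes uncertainty that more data would reduce, whereas this quantity is not identified at any sample size. No section limits H4's second sentence to prediction.

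**The limitation is shared by H1 to H3, which also rest on time as treatment.** This stands. H4 still merits its own correction, because it places the moderation claim beside a prognostic claim that the design can test.

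**The rates are invented and mostly generous.** This stands in part. Return rates, the baseline distribution, the even split and the all-or-nothing post score are assumptions, and graded return is not modelled. Small gaps and the planned correction bring the rates down a good deal, though in every scenario with a prognostic gap they remain above nominal (5% against 1% in the mildest case).

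**Stronger readings that the documents do not support:**

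- *The interaction shows nothing but prognosis.* It may also contain true modification. The design cannot isolate it.
- *The background establishes a difference in return among untreated people over 12 weeks.* It gives a direction, with no time horizon, strength or treatment status. A slower natural course is a plausible rival explanation, not a documented one.
- *All of RQ2 and Paper II must become predictors of outcome.* RQ2 also covers adherence, which exists only under treatment. H5b and H7 concern mediation. H8 concerns moderation between measured variables among treated people, to which this argument does not apply.
- *H4 will decide who is offered the program.* No section says so.

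**Conclusion.** The concern holds for the second sentence of H4. With one treated arm and treatment entered as time, the planned interaction cannot separate a smaller program effect after long absence from a slower natural return, so H4 can be confirmed when the program adds nothing. That conclusion follows from the design and needs no assumed figure.

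Its size does need one. For gaps of 5 to 20 points in natural return, zero treatment effect and 273 completers, false confirmation runs from about 14% to 94% at 0.05 and from about 5% to 82% at an assumed 0.01. No single value in that range should be quoted as the trial's error rate. The first sentence of H4 is a prognostic hypothesis and can be tested as written.

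**What to change.** 1. In H4, delete the second sentence and keep the first, or replace the second with: *baseline absenteeism will predict the course of sick leave among treated participants*.
2. In Statistical analyses, label the interaction of time with baseline absenteeism as a predictor of course.
3. State there that no conclusion about who benefits more or less from the program will be drawn from this term, and carry that statement into Paper II.

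The adherence part of RQ2, the mediation hypotheses and H8 need no rewording on this ground.

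Cost: a few lines of protocol text, with no change to data collection, sample size or model. The downside is a less ambitious claim. Keeping the moderation claim would instead require a comparator, which is a different study.

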*Secondary outcome measures:* The Generalized Anxiety Disorder-7 (GAD-7; (Spitzer et al. 2006) is a measure of worry and anxiety and consists of seven items scored from 0 (“Not at all”) to 3 (“Nearly every day”) and one additional item measuring how the symptoms affect functioning. The Patient Health Questionnaire-9 (PHQ-9; (Kroenke, Spitzer & Williams 2001) measures depression severity. The measure consists of nine items scored from 0 (“Not at all”) to 3 (“Nearly every day”). The Work and Social Adjustment Scale (WSAS; (Mundt et al. 2002) measures impairment in functioning. The measure consists of five items scored from 0 (not at all impaired) to 8 (very severely impaired). CORE-OM (Evans et al. 2002) is a 34-item self-report, measuring well-being, symptoms, elements of risk, and function on a five-point scale ranging from “not at all” to “most, or all the time”. CORE-10 (Barkham et al. 2013) is a ten item self-report measuring symptoms, well-being, functioning and risk on a five-point scale ranging from “not at all” to “most, or all the time”. The Negative Effects Questionnaire (NEQ) (Rozental et al. 2016, Rozental et al. 2019) is a 20-item questionnaire evaluating adverse or unwanted events during treatment. Participants report whether a specific event occurred during treatment (“Yes”/”No”) and then indicate how negatively they were affected by it on a scale ranging from 0-4. An adapted version of the Credibility Rating Scale (Borkovec & Nau 1972) will be used to assess treatment credibility. The scale consists of five items where participants rate their credibility/expectancy-for-improvement on a 10-point scale.

**System data on user behaviour.** Data on use and user behaviour will be extracted from the system and combined with data from the self-report questionnaires collected. Information about the actual program use will be generated by the e-health platform Youwell. The data includes the extent to which participants complete the treatment, where and when they drop out, and how long they need to complete individual parts. Further we will look into whether there are areas in the treatment that require more time than others, which elements are used

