## Power analyses

In a multilevel model, the fixed effects are comparable to ordinary repeated t-tests, and thus, using this as a proxy model with a moderate effect size ( $d = 0.6$ ), power = 0.8, alpha = 0.05, tails = "two.sided", we need 25 subjects for detecting a single main effect Murayama, Usami and Sakaki (2022); see [Summary-statistics-based power analysis \(shinyapps.io\)](#). But, as stated by Van Voorhis and Morgan (2007): "*if the circumstances allow, a researcher would have better power to detect a small effect size with approximately 30 participants per variable*" (page 48). Following this rule of thumb, we plan for 30 participants per predictor (unique main effects), thus a total sample size of 300 participants. Calculating a drop-out rate of 30% gives a total sample size of  $N = 390$ . Calculating power for indirect effects – or mediation – we used the following online shiny app [Monte Carlo Power Analysis for Indirect Effects \(shinyapps.io\)](#), published by Schoemann, Boulton and Short (2023). Using (El Alaoui et al. 2015) as a proxy study for the direction and strength of association between our variables, they found that both treatment credibility and treatment adherence were significantly predictors of faster change and lower post treatment scores in a routine psychiatric care based ICBT for social anxiety disorder. In the same study, a high level of treatment credibility was associated with higher treatment adherence. Hence, defining X = treatment credibility, M = treatment adherence and Y = treatment outcomes, we set the correlation of X-M (a-path) = 0.3 ( $SD = 1$ ), X-Y (c-path) = 0.30 ( $SD = 1$ ) and M-Y (b-path) = 0.30 ( $SD = 1$ ), power = 0.8, alpha = 0.05, setting random seed to "0512", using 5000 replications with 20000 Monte Carlo draws per replication, we need  $N = 155$  to have a power of 0.80, 95% CI [0.79-0.82].

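### H9 sets a 10% limit on negative effects caused by participation, but the NEQ as the protocol describes it records nothing about cause

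*Protocol*

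**What the plan says.** H9 reads: "We expect that fewer than 10% of participants experience negative effects caused by participation". It names the instrument in the same sentence: "as measured by the Negative Effects Questionnaire (NEQ".

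The Measures section (secondary outcome measures) says that the NEQ "is a 20-item questionnaire evaluating adverse or unwanted events during treatment". It then describes two answers per item. The first is occurrence: "Participants report whether a specific event occurred during treatment", answered Yes or No. The second is impact: participants "indicate how negatively they were affected by it on a scale ranging from 0-4". It describes no third answer on what brought the event about.

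On design, the protocol says: "This study is a non-randomized, single arm, multi-center mixed methods clinical trial in a naturalistic setting". The matching research question is purely descriptive: "What type and frequency of negative effects does participants report".

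The Power analyses section plans for loss ("Calculating a drop-out rate of 30" per cent). The section on participant drop-out covers the offer of other treatment and mentions no questionnaire. No time point specific to the NEQ is given in the text.

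**The concern.** H9 puts a number on a causal quantity, while the instrument as described measures timing and impact. An event that occurs during treatment may come from the programme, the illness, the workplace or life in general. The participants are outpatients in specialised mental health care who are on sick leave or work assessment allowance, so unrelated adverse events are plausible.

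H9 is the only hypothesis on harm, and the Knowledge gap section gives poor past assessment of negative effects as one reason for the study. If attribution is not asked when the form is filled in, it is lost. H9 could then appear refuted because of events unrelated to the programme, or be answered with a figure that is not the one it names. H9 also does not say which answer, at what impact level, makes a participant a case, so the 10% has no defined numerator.

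A second, weaker worry is that people who leave the programme may be under-represented among those who answer.

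**Working it through.** **1. Hypothesis and measure side by side**

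| Element | H9 | NEQ as described in Measures |
|---|---|---|
| Event | negative effect | adverse or unwanted event, 20 items |
| Link to the programme | caused by taking part | happened while in treatment |
| Impact | no level stated | 0 to 4 |
| Attribution | required | not described |

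Cause could come from an attribution answer or from a comparison group. The first is not described, and the single-arm design rules out the second.

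**2. How much unattributed events could matter (illustration only)**

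Assumptions, none of them in the protocol: any Yes counts, items are independent, and each item has the same rate p of events unrelated to the programme. The share of participants with at least one Yes is 1 − (1 − p)^20.

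- p = 0.5%: 1 − 0.995^20 = 9.5%
- p = 0.53%: 10%, from p = 1 − 0.9^(1/20) = 0.00525
- p = 1%: 1 − 0.99^20 = 18.2%
- p = 2%: 1 − 0.98^20 = 33.2%

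Positive correlation between items would lower these shares, and so would a minimum impact level. The point is only that 20 items need very small unrelated rates to reach 10%.

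**3. Number likely to answer**

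H9 has no sample size of its own. The protocol's total reproduces as 300 × 1.30 = 390. Losing 30% of 390 leaves 390 × 0.70 = 273.

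**4. Sensitivity to drop-out (assumed rates)**

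If 30% do not answer, the overall rate is 0.7 × (rate in responders) + 0.3 × (rate in non-responders).

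- Responders 8%, non-responders 20%: 0.7 × 0.08 + 0.3 × 0.20 = 11.6%.
- With 8% in responders, the overall rate reaches 10% when non-responders are at (0.10 − 0.7 × 0.08)/0.3 = 14.7%.
- With 5% in responders, it does so at (0.10 − 0.7 × 0.05)/0.3 = 21.7%.

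**5. Precision and denominator (exact Clopper-Pearson limits)**

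- 25/273 = 9.2%: 95% CI 6.0% to 13.2%.
- 27/273 = 9.9%: 95% CI 6.6% to 14.1%.
- The same 27 events over all 390, with non-responders taken as event-free: 27/390 = 6.9%, upper limit 9.9%.

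The last two lines show that treating silence as absence of harm moves the upper limit from well above 10% to just below it, with no new information.

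**The case against.** The Measures section is a short summary of a published questionnaire. The version in use may carry an attribution answer that the summary omits. This stands, so it would be wrong to infer that the NEQ itself cannot attribute events. If it does, however, the description is incomplete and H9 should name the answer it relies on.

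The protocol does not say that any Yes will count, and the per-item rates above are assumed. This also stands: they show sensitivity and are not estimates.

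A reader might infer that the NEQ is answered mainly by those who stay. The documents do not say so. The Design section lists pre, interim, post and follow-up collection, the 6- and 12-month questionnaires are requested from participants by SMS, and nothing states that people who stop treatment are left out. The 30% is a sample-size allowance, and greater harm among drop-outs is an assumption. What remains is a risk: no NEQ collection from drop-outs is described.

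A reader might also infer that H9 will be declared confirmed whenever the observed rate is under 10%. The protocol states no such rule, H9 is worded as an expectation, and the rule may stand in an analysis plan not shown here. Requiring an upper confidence limit below 10% would be a choice with a price. At n = 273 the two-sided 95% limit allows at most 17 cases (6.2%), and H9 would be confirmed only 36% of the time if the true rate were 7%.

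Finally, H9 is not the safety system. Weekly monitoring of suicidal ideation and CORE-10 with automatic alerts runs separately and is untouched by this point.

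**Conclusion.** The point holds for attribution. As described, the NEQ yields the share of participants with events during treatment, and neither the questionnaire nor the single-arm design turns that into the share with effects caused by the programme. This rests on the protocol's own wording and needs no numerical assumption.

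The possible size of the gap does rest on assumptions. Under independent items and an any-Yes rule, about 0.53% per item is enough to reach 10%. Under-representation of drop-outs is a risk worth guarding against but not a documented fact, and no error can be charged to the protocol over a decision rule it does not state. The matter is worth correcting because it concerns the only harm hypothesis and cannot be repaired after data collection. It does not affect the work or symptom outcomes.

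**What to change.** **Main change.** Define an H9 case as a participant with at least one NEQ item answered Yes and attributed by the participant to the programme, at a stated impact level. If the version in use already has an attribution answer, use it and correct the Measures section. If not, add one yes/no question per endorsed item. If neither is possible, reword H9 to negative effects reported during treatment, which would agree with the research question on type and frequency. In either case, report participant attribution as perceived cause, since a single-arm trial cannot establish more.

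**Safeguard.** Also send the NEQ automatically when a participant drops out. Report the rate among responders with its exact 95% CI, and add a sensitivity analysis over plausible rates in non-responders using the formula above. Never count non-responders as event-free.

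**Cost.** One extra tick per endorsed item and one automatic questionnaire at drop-out. Sample size and treatment procedures do not change.
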